**History of protocol amendments approved by McGill University's Research Ethics Board**

(Refer to Appendix 1):

- Recruitment age increased from 18-26 years to 18-40 years (approved April 14, 2014).
- Maximum duration of relationship increased from 3 to 6 months (approved April 30, 2014).
- Compensation increased from CAD 350 to CAD 500 per couple (approved February 9, 2015). The above protocol changes were made to improve recruitment and/or simplify the logistics of the study.
- Gardasil 9 as intervention vaccine: The additional amendment relating to Gardasil 9 will enhance the health benefit of the study to participants while making this protocol truly cutting-edge with respect to the state of HPV science (approved July 08, 2015).
- Recruitment age increased from 18-40 years to 18-45 years (approved February 16, 2016).
- Discontinuing anal sampling: potential and current participants have confirmed our suspicions that troubling recruitment rates are due partially to the embarrassing and uncomfortable nature of this procedure (approved July 14, 2016).
- Adding a recruitment site in New York to increase the rate of accrual of participants (approved April 3, 2017).
- Compensation increase from CAD 500 to CAD 1000 per couple (approved May 8, 2017)
- Switch the placebo vaccine from Havrix to Avaxim (requested June 4, 2018, approved June 12, 2018).
- Second Oral Tube Collected: [name] transfers the sample to a freezer tube with tampon (she calls it "TE") - [name] removes the residues of the mouthwash and re-suspends it in the tampon. It's all kept in the freezer at [name] lab (information collected with [name] on February 11, 2022).
- Close study recruitment at 188 couples instead of the original 500 couples (requested on March 31, 2022, approved on May 26, 2022)
- Use of a different assay for serology testing (requested on September 8, 2022, approved on September 12, 2022) (Refer to Appendix 2)

## 1. The Need for a Trial

### 1.1 What is the problem to be addressed?

Two prophylactic vaccines (Gardasil, a quadrivalent vaccine by Merck, and Cervarix, a bivalent one by GlaxoSmithKline [GSK]) have been proven in randomized controlled trials (RCT) to be highly effective in preventing infection with the vaccine target HPV types (HPV-6/11/16/18, for Gardasil, and HPV-16/18, for Cervarix) and the cervical precancerous lesions caused by them. These vaccines have shifted the paradigm of prevention measures and are expected to have a major impact in reducing the burden of cervical cancer and other HPV-associated malignancies, such as vulvar, vaginal, penile, anal, and oropharyngeal cancers, as well as benign HPV-associated conditions (in the case of Gardasil), such as anogenital warts and respiratory papillomatosis.

Vaccination programs aim to be cost-effective by reaching sufficiently high coverage to reduce transmission to levels that are low enough to permit protection to extend also to susceptible, unvaccinated individuals, a concept broadly designated as herd immunity. Given the long timescales involved, mathematical models have played an important role in predicting herd immunity thresholds and informing policy decisions regarding HPV vaccination strategies. The results of published health economic models on the impact of HPV vaccination have consistently shown that delivery of HPV vaccination is cost-effective. Studies of the impact of HPV vaccination of 12-year-old girls in North America estimated a cost-effective ratio ranging from \$31,000 - \$43,600 per quality-adjusted life-year gained, compared with current screening. The added benefits of vaccinating boys have been also evaluated with mixed results. Most recently, we concluded that the potential incremental gains of vaccinating boys may be limited because of the predicted herd immunity impact of vaccinating girls under moderate to high vaccine coverage. However, differences in model structure and assumptions have made it difficult to compare the findings across studies and apply them to policy evaluations. HPV transmission dynamics have been identified as a key source of heterogeneity in health economic studies of the impact of HPV vaccination. In summary, whether or not provinces should implement vaccination of boys has to rely on such health economic models, but the latter require knowledge of empirically-derived estimates of how vaccination prevents transmission between partners. No vaccination study has yet derived these estimates.

### 1.2 What is/are the principal research question(s) to be addressed?

Much remains to be understood on the effects of HPV vaccination in preventing transmission of target HPV types to sexual partners of vaccinated individuals and its impact on herd immunity. Does vaccination of unexposed persons against HPV infection effectively protect their sexual partners from HPV infection? The published RCT data has been unequivocal in that vaccination seems to be exclusively prophylactic, i.e., it does not help to clear preexisting HPV infections in an individual. However, it is not known whether or not such a previously infected individual, once vaccinated, would be less infective to her or his sexual partner. Likewise, does vaccination protect against HPV infection with the target types in mucosal sites other than the cervix? Apart from the knowledge from Gardasil RCTs that focused on the female lower genital tract, no information is available concerning whether pan-mucosal protection (via exudation of neutralizing antibodies) leads to decreased HPV transmission risk.

Would the efficacy of vaccination in preventing transmission of HPV 6/11/16/18 warrant a two-gender vaccination strategy? This question has been the focus of much research on mathematical modeling of the cost-effectiveness of HPV vaccination and policy discussions. Thus far, there is no empirical evidence for answering the above question, other than the knowledge that the vaccine is efficacious in women and also in men.

The objective of this study (TRAP-HPV) is to shed light into the effect of an HPV vaccine (Gardasil) in preventing transmission of target HPV types to heterosexual partners among young sexually active couples in Montreal. Specifically, TRAP-HPV aims to determine the efficacy of an HPV vaccine in reducing transmission of genital, anal, and oral HPV infection in sexual partners of vaccinated individuals.

**1.3 Why is a trial needed now? Evidence from the literature - see 1.4 below, professional and consumer consensus and pilot studies should be cited if available.**

This proposal describes an RCT that aims at measuring the impact of vaccination in preventing HPV transmission to sexual partners of young, sexually-active university students in Montreal. Valuable data will be collected on HPV transmission dynamics of both women and men with either incident or prevalent infections of HPV 6/11/16/18 at multiple infection sites. The information provided from this study could potentially have large public health implications by providing proof of concept and empirical data to inform new effective policies and vaccination programs aimed a population level.

**1.4 Give references to any relevant systematic review(s) and discuss the need for your trial in the light of the(se) review(s). If you believe that no relevant previous trials have been done, give details of your search strategy for existing trials.**

On 8 August, 2012, we searched the PubMed online database with keywords 'HPV' AND 'vaccine' AND 'transmission'. This search returned with only two references. One study reviews the importance of using condoms in reducing STD transmission. The second study tests the immunogenicity and protective efficacy of a vaccine to reduce the transmission of both HPV and the Human Immunodeficiency Virus (HIV) among macaques. No clinical trials on this topic are currently registered in the clinical trials registries (ClinicalTrials.gov and ISRCTN). Our inquiries to Merck and GSK indicates that no such study is being done or planned, as these two companies would have to be involved to provide vaccines. Finally, we have scanned all abstracts submitted to the past 6 International Papillomavirus Conferences (and actually attended them); no study has sought to obtain proof of concept for a transmission prevention effect consequent to HPV vaccination. Obtaining such proof would provide valuable insights and empirical data to inform the mathematical modeling of HPV vaccination strategies.

**1.5 How will the results of this trial be used? E.g. inform decision making/improve understanding.**

At this time there is no way to treat cervical HPV infections. As described above, we do not know whether HPV vaccination is effective in blocking transmission, or preventing the acquisition of HPV infection in anatomical sites other than the cervix. If any additional effect for the HPV vaccine is proven, this will be used as new empirical evidence for mathematical models of vaccination that are used by policymakers in Canada and elsewhere. Our own CIHR Team (CRN-83320) includes a health economics component (led by [name] [appended letter]), which will enable us to quickly move to a knowledge translation activity when the results become

available. So far, models that gauge the potential impact of vaccinating boys have not taken into account the impact of the vaccine in reducing transmission between partners and, within the same partner, to other mucosal sites.

### **1.6 Describe any risks to the safety of participants involved in the trial.**

Gardasil was approved in Canada for women aged 9-45 years and for men aged 9-26 years. Its safety was studied in over 29,000 males and females, in several trials before licensure in 2006. The U.S. Centers for Diseases Control and Prevention (CDC) and the U.S Food and Drug Administration (FDA) maintain a sentinel public health system called Vaccine Adverse Event Reporting System (VAERS). By 15 September 2011, 40 million doses of the Gardasil vaccine had been distributed in the US. The rates of adverse events following Gardasil in VAERS are comparable to those for other vaccines, except for syncope and venous thromboembolic events. Another study by a network of managed care organizations in the US found no statistically significant increases in risk of adverse events, except for venous thromboembolism. In all such cases risk factors were present (obesity, oral contraceptive use, smoking, recent hospitalization, or coagulation disorders). The Public Health Agency of Canada states that both HPV vaccines available in Canada are safe; the most common side effect being pain at the site of injection.

## **2. The Proposed Trial**

### **2.1 What is the proposed trial design? E.g. Open-label, double or single blinded, etc.**

TRAP-HPV will be a randomized, placebo-controlled, double-blinded controlled trial to investigate the impact of Gardasil vaccination on the transmission of HPV infection to sexual partners in heterosexual couples ages 18-40 years living in Montreal.

### **2.2 What are the planned trial interventions? Both experimental and control.**

Once recruited, both individuals in a couple will be randomized independently to treatment or placebo (table 1). Treatment is defined as vaccination with Gardasil (Merck). *This vaccine was chosen because it allows for the observation of 4 HPV outcomes (HPV 6, 11, 16, & 18)* (the other available vaccine, Cervarix, protects against HPVs 16 and 18, only). The existing public HPV vaccination program in Quebec does not include women targeted by our study (aged 18-40) or men of any ages. Therefore, we expect low uptake of opportunistic HPV vaccination in the subjects eligible to be enrolled in this study; rates of Gardasil immunization among these subjects will be very low.

The placebo vaccine will be a hepatitis A vaccine, Havrix (GSK). This control vaccine was chosen because hepatitis A immunization provides a similar health prevention incentive as HPV vaccination to study participants while preserving the scientific cogency of a “placebo” comparator. Gardasil requires administration of 3 doses, while Havrix only requires 2 doses. For this reason, we will add a placebo injection (saline solution) in between the Havrix vaccination regimen. Consequently, both treatment and control vaccines will have similar regimens, i.e., study entry, 2 months, and 6 months. As detailed in table 1, four comparison groups will be formed via a 2-by-2 design where partners will both have been vaccinated with Gardasil or with Havrix or will have unequal vaccination treatments. Comparing combinations of these 4 groups will yield valuable information on the effect of vaccination on HPV transmission blockage.

**Table 1: Four vaccination comparison groups in 2x2 factorial design**

Female (F) vaccination	Male (M) vaccination	
	HPV (Gardasil) (T)	Placebo (Havrix) (P)
HPV (Gardasil) (T)	M T F T	M P F T
Placebo (Havrix) (P)	M T F P	M P F P

In order to ensure that all study participants gain similar health benefits and incentives in keeping with ethical values, we will use a crossover of interventions at the end of the study by offering Gardasil to all control subjects and Havrix to all HPV-immunized subjects. The benefit of HPV vaccination would not be significantly delayed for control subjects since the study is relatively short (12 months). Furthermore, the control subjects at risk of HPV infection will benefit from our intensive follow-up protocol which would provide substantial protection and surveillance of HPV infection that extend beyond those given by standard care. All women with persistent HPV infections with oncogenic HPV types will be offered a Pap test. At the end of TRAP-HPV, an exit Pap test will be given to all female participants. Since there are no guidelines for screening men, only male subjects who appear to have visible lesions will be referred for clinical examination.

**2.3 What are the proposed practical arrangements for allocating participants to trial groups? E.g. Randomization method. If stratification or minimization is to be used, give reasons and factors to be included.**

Assignment of the vaccine will be done by the coordination centre at McGill by computer-assisted block randomization with randomly variable block sizes. Please refer to section 3.1 for more information regarding the arrangements for enrolment and randomization.

**2.4 What are the proposed methods for protecting against sources of bias? E.g. blinding or masking. If blinding is not possible please explain why and give details of alternative methods proposed, or implications for interpretation of the trial's results.**

Participant blinding is assured because both vaccines (HPV and hepatitis A) and their syringes will look identical (previously drawn from blinded vials in a separate room by the nurse). Furthermore, injection pain is expected to be the same for both vaccines. To maximize retention, every effort will be made to enrol only eligible and motivated couples. Issues regarding recruitment, compliance and loss to follow up are described in more detail in sections 2.12-2.14.

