All study participants (both genders) will provide anal swab specimens for HPV testing on all six study visits (Figure 1). Lampinen et al. developed feasible, simple illustrated instructions for self-collecting anal swabs. Study participants will be instructed to remove clothes from the waist down, remove the swab from the wrapping, and choose a comfortable position, e.g. by standing with one foot on a stool, to facilitate access to the anus. The subject will be asked to hold one buttock to one side. Then the subject will hold the swab 3-4 cm from the tip. They will have to hold the swab firmly and gently insert it into their anus (3-4 cm) until the tips of their fingers touch the outside of their anus. They will need to release their hold on the shaft, then take hold of the swab again, about halfway down the shaft. The swab is to be moved once in a large circle, pressing gently against the inside of their anus. Then the swab will be, slowly and gently, removed from their anus and turned slowly as they remove it. The swab will then be placed into a UCM-containing collection vial.

*Self-administered web-based questionnaire (please see appendix)*

We will use a secure, confidential study-designated Internet site to provide participants with protected access to the web-based questionnaire by assigned login names and passwords. At induction, males and female subjects will learn to use the web-based system using computers at the clinic sites. At that time they will complete their enrolment questionnaire. Subsequently, all participants will complete five follow-up questionnaires (months 2, 4, 6, 9 and 12).

*Randomization Strategy*

Eligible couples will be recruited into each centre and treatment assignment will apply to a couple as a unit. Randomization of the study participants will be done via a computer-assisted block randomization with randomly variable block sizes at the coordination centre at McGill University. Treatment assignment will be given to the study coordinator at a centre via a secure web-based program at the time the couple is enrolled. To ensure participant blinding, vaccine vials will be masked and look identical so that both the participant and the nurse administering the vaccine will be unaware of their content. This will also ensure that both partners will not know whether they have received Gardasil or Havrix.

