## **2.16 What is the proposed type of analyses?**

### *Statistical Analysis*

We hypothesize that HPV vaccination is effective in reducing the risk of HPV transmission to their sexual partners. The above plan takes advantage of the opportunity for measuring transmission events in multiple mucosal sites for multiple HPV types, over multiple clinic visits, and in both directions (i.e., male-to-female and female-to-male). We will take advantage of advanced regression methods as framework for measuring the effects expected via HPV vaccination.

In the simplest core formulation (e.g. analyzing a single HPV type and a single mucosal site), we will use the Kaplan-Meier technique to plot the cumulative probability of HPV infection in sexual partners of vaccinated versus unvaccinated individuals against follow-up time. Using the layout in table 1, this implies comparing the HPV infection histories of women in the  $M^T F^P$  and  $M^P F^P$  groups and of men in the  $M^P F^T$  and  $M^T F^P$  groups. Expectedly, protection is also likely to occur via cumulative effects observable via HPV DNA detection in multiple mucosal sites. Similar time-to-event analyses will be conducted to examine these pan-mucosal site effects.

Statistical comparisons in the HPV transmission between vaccine and control groups will be determined using the log-rank test. The Cox proportional hazard regression model will be used to estimate the effect of vaccination on transmission of HPV to sexual partners. Time to HPV infection will be defined in days as the time from study enrolment to the date of infection. Hazard ratios (HR) and their respective 95% confidence intervals will be computed. Statistical analyses will follow an intention-to-treat approach but additional regression models will examine the role of several candidate determinants in mediating transmission and the protective effects.

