### Maximum duration of relationship for eligible couples was increased from 3 to 6 months

Although the likelihood that transmission of HPV has already occurred becomes greater with longer duration of relationship, evidence from a recent couple's study conducted by our division (HITCH study) indicates that new HPV infections are still very common among young couples reporting being involved in a sexual relationship for up to 6 months.

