#### **Age range for eligible couples was increased from 18-40 to 18-45 years**

The National Advisory Committee on Immunization (NACI) recommends the use of Gardasil in females aged 9-45. Studies have shown the vaccine to be safe and efficacious in older females and males. Although females <25 are at the highest risk of HPV, those older than 25 remain at risk and the risk among males is not associated with age but remains high throughout life. Based on this, increasing the age range for eligible couples is safe and will further improve our potential for recruitment.

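### The primary comparison in section 2.16 names no baseline covariates although eligibility was widened on factors the protocol itself links to HPV risk or prior transmission; a short pre-specified adjustment would recover some power

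*Combined protocol and SAP*

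**What the plan says.** **Allocation.** Section 2.3 describes "computer-assisted block randomization with randomly variable block sizes". Its heading includes the prompt "If stratification or minimization is to be used, give reasons and factors to be included", and the answer names none. The Randomization Strategy paragraph in section 2.9 repeats the method and says "treatment assignment will apply to a couple as a unit" (section 2.2 instead has partners randomised independently), again without a factor. The readable part of section 3.1 adds nothing.

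**Widened eligibility.** The amendment history records "Maximum duration of relationship increased from 3 to 6 months" and, after an earlier move from 26 to 40 years, "Recruitment age increased from 18-40 years to 18-45 years". A site recruiting through Rutgers clinics was also added.

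**What the justifications in Appendix 1 say.** On age: "females <25 are at the highest risk of HPV". The same sentence adds that risk in men is unrelated to age and stays high. On duration: "the likelihood that transmission of HPV has already occurred becomes greater with longer duration of relationship". That sentence goes on to say that new infections remain very common up to six months.

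**Analysis.** Section 2.16 states: "Statistical comparisons in the HPV transmission between vaccine and control groups will be determined using the log-rank test". A Cox model estimates the vaccination effect, with no covariates listed. Other variables appear only in additional regression models of unnamed determinants. Elsewhere, section 2.8 promises to take enrolment infection status into account, without a method. The Gardasil 9 justification in Appendix 1 promises analyses stratified by prior HPV vaccination. Section 2.16 takes up neither promise.

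**The concern.** When baseline variables predict the outcome, an analysis that ignores them discards information. In a time-to-event analysis this lowers power even when the arms are perfectly balanced. In small groups it also leaves the one realised estimate exposed to chance differences in those variables. Here the entry criteria were relaxed in ways that probably make participants more varied at baseline, while the analysis text was not revisited.

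The trial closed at 188 couples instead of 500, about 47 per cell if allocation was equal. Recruitment is over, so allocation can no longer be stratified and analysis is the only lever left. There is a second cost. Promises to consider enrolment status and prior vaccination, with no stated model, leave the covariates to be chosen after results are seen.

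**Working it through.** **1. The plan's own sample size.** Inputs from section 2.11: 3.8 acquisitions per 100 subject-months, 12 months, one-sided 0.05, 16% loss.

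- Control risk p1 = 1 − exp(−0.456) = 36.6%. Treated risk p2 = 1 − (1 − p1)^HR.
- n per arm = (z_α + z_β)² × (1/p1 + 1/p2) / ln(HR)². For a 40% reduction at 80% power this gives 163.7.
- Halving for pooled sexes gives 81.8; dividing by 0.84 for losses gives 97.4 (stated 97).
- The same steps give 81.0 (stated 80) and 58.5 (stated 59) for a 50% reduction at 90% and 80% power.

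Pooling and loss inflation are inferred, since the text does not state them. The calculation uses a single control hazard and makes no allowance for differences between participants.

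**2. Events available at 188 couples.** Per cell: 188/4 = 47. With HR 0.5 and no losses, a single-sex contrast yields 47 × (1 − exp(−0.456)) + 47 × (1 − exp(−0.228)) = 17.2 + 9.6, about 27 events. Pooling the sexes gives 94 per arm and about 54 events. Losses would lower both.

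**3. Power without and with adjustment.** Simulated trials: control rate 3.8 per 100 subject-months, HR 0.5, 12 months, one-sided 0.05, no losses, one summary covariate. The log-hazard SD is the assumed combined strength of the enrolment predictors. Two independent sets were run, of 1,500 and 2,500 trials per setting.

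| Log-hazard SD | 47 per arm, set 1 | 47 per arm, set 2 | 94 per arm, set 1 | 94 per arm, set 2 |
|---|---|---|---|---|
| 0.5 | 53% to 54% | 49% to 52% | 77% to 80% | 77% to 79% |
| 0.7 | 46% to 49% | 46% to 51% | 72% to 78% | 71% to 77% |
| 1.0 | 39% to 47% | 39% to 48% | 64% to 75% | 63% to 74% |

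A third simulation, with four covariates and 16% loss, gave gains of about 0 to 4 points at SD 0.35 to 0.5 and 6 to 8 points at SD 0.7 to 1.0. Type I error was about 5 to 6%.

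A stratified log-rank check used HR 0.6, 16% loss and a binary factor with 50% prevalence. Such a factor has log-hazard SD ln(HR)/2, that is 0.35 for a factor HR of 2 and 0.55 for 3. Power moved from 35.2% to 36.0% (factor HR 2) and from 33.7% to 35.3% (factor HR 3) at 47 per arm. At 94 per arm it moved from 55.1% to 56.0% and from 54.3% to 57.1%. No gain was detectable at a factor HR of 1.5.

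**4. Validity and chance imbalance.** Type I error of the unadjusted test was 4.5 to 5.7%. At 47 per arm, imbalance moves the unadjusted log hazard ratio with SD = (log-hazard SD) × √(2/47): 0.10 at 0.5, 0.14 at 0.7 and 0.21 at 1.0, which are factors of 1.11 to 1.23. The standard error of the log hazard ratio is √(1/17.2 + 1/9.6) = 0.40.

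For a binary factor, the 95th percentile of imbalance at 47 per arm is about 20 percentage points. The shift in the hazard ratio is then (1 + 0.6(h − 1)) / (1 + 0.4(h − 1)), where h is the factor's hazard ratio: 1.08 for h = 1.5, 1.14 for 2 and 1.22 for 3.

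**The case against.** The case for leaving the plan alone has real substance.

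- **Age and duration.** A reader might infer that the protocol calls both prognostic for everyone. It does not. It says male risk is unrelated to age, and half the potential recipients are men. On duration it speaks of transmission that has already happened, which acts mainly through enrolment infection status. This stands, and it is why infection status heads the covariate list and age has separate slopes.
- **Adjustment already foreseen.** Section 2.8 and Appendix 1 do promise attention to infection status and stratification by prior vaccination, so the plan is not wholly unadjusted. But neither names age, duration or site, and the first has no method.
- **Section 2.3.** Its prompt is conditional, so naming no factor is a permitted answer. In simulation, stratifying the randomisation made no difference beyond simulation error.
- **Bias.** A reader might infer that the unadjusted test is invalid or its estimate wrong. Randomisation protects the test. At SD 1.0 the median unadjusted hazard ratio was 0.54, against 0.49 adjusted and a conditional truth of 0.50. That gap reflects marginal and conditional hazard ratios being different quantities. Imbalance is a minor part of a standard error of 0.40.
- **Assumed strength.** SDs of 0.7 and 1.0 correspond to 50/50 binary factors with hazard ratios of about 4.1 and 7.4. Nothing in the documents shows predictors that strong. This stands.

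**Conclusion.** The point holds as a worthwhile improvement in efficiency and pre-specification; the planned test is not in error. The gain is about 0 to 4 points of power at log-hazard SD 0.35 to 0.5 and about 6 to 11 points at 0.7 to 1.0. In the two one-covariate simulations, a single-sex contrast at SD 0.7 gained only 3 to 5. These figures assume equal cells, a 50% reduction, proportional hazards and covariates entered in the correct form. The prognostic strength is assumed throughout.

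A reader might infer that adjustment can make good the recruitment shortfall. It cannot. For a 40% reduction, power at 188 couples is about 61% with sexes pooled and 39% for one sex, before losses, against the 80% that section 2.11 attaches to 97 couples per group.

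Unstratified means only that no stratification is stated in the available text; some pages are not public.

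**What to change.** In section 2.16, before unblinding, make the primary estimate a Cox model for the randomised contrast with a fixed covariate list:

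- enrolment HPV DNA status of recipient and partner for the vaccine types, which gives the promise in section 2.8 a method;
- relationship duration at enrolment, continuous;
- age, continuous, with separate slopes for women and men;
- prior HPV vaccination or baseline seropositivity, type-specific in type-level models and for any vaccine type in the any-type analysis.

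Stratify by site only if Rutgers enrolled enough couples. Keep the unadjusted log-rank test and Kaplan-Meier curves as supporting analyses.

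The list has to stay short. In a single-sex contrast it means five covariates plus treatment: 27/6 = 4.5 events per parameter. Either trim it or pool the sexes. Pooled and stratified by sex, with two age slopes, there are seven parameters: 54/7 = 7.7. If pooled, use a variance that allows for both partners of placebo-placebo couples entering the control arm.

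The cost is mainly wording. Age and relationship duration are screened at entry, and HPV DNA testing at enrolment and serology are already planned, although Appendix 2 describes the new serology assay as still to be done. The adjusted hazard ratio is conditional on the covariates and should be labelled so, beside the unadjusted one.
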